9.5.3 Criteria for determining the causality between AEs and investigational drugs

- Definitely related: The reaction occurs in a plausible time relationship to drug administration. The reaction is a recognized pharmacological phenomenon of the investigational drug. The reaction improves on drug discontinuation and reappears when the drug is given again.
- Possibly related: The reaction occurs in a plausible time relationship to drug administration. The reaction is a recognized pharmacological phenomenon of the investigational drug. The clinical state of the subject or other treatments may also produce this reaction.
- Possibly unrelated: The reaction does not occur in a plausible time relationship to drug administration and does not match the type of reaction known to the investigational drug. The clinical state of the subject or other treatments may also produce this reaction.
- Definitely unrelated: The reaction does not occur in a plausible time relationship to drug administration. The reaction is a recognized pharmacological phenomenon of the non-investigational drug and can also be explained by the subject's clinical status or other treatments. The reaction disappears on disease improvement or discontinuation of other treatments, and repeated use of other treatments causes this reaction to occur.
- Not assessable: There is no clear relationship between the time of onset of reaction and time of drug administration. The reaction is similar to the recognized pharmacological phenomenon of the investigational drug. The clinical state of the subject or other treatments may also produce this reaction.

9.5.4. Documentation and reporting of adverse reactions

The specific description of the AE, its time of onset, end time, severity, frequency, and whether treatment is required (if required, please record all administered treatments), and correlation between the AE and the investigational drug as judged by the investigator should be recorded in detail.

When an AE occurs, the observing physician can decide whether to terminate observation based on the patient's condition, and an adverse event should be followed up until it resolves. Medical documents related to adverse events should be recorded in the source document, including notification forms for laboratory tests (such as X-ray, electrocardiography), and test results slip. If the subject is unable to continue receiving treatment with the investigational drug due to trial completion or subject discharge from the hospital, the investigator should submit the case summary of the subject (including descriptions of treatment arrangements and whether adverse event follow-up is required) to the physician that is responsible for treating the subject. This information will also be recorded in the source document.

When an SAE occurs, the principal investigator and the institution must be immediately notified by phone within 24 hours regardless of whether there is a close relationship with the investigational drug. The "Serious adverse event (SAE) report" should be filled in, signed, and dated. The SAE report will immediately be faxed to the Ethics committee, NMPA, and the regulatory authority of the region where the investigator is located. The symptoms, severity, time of onset, time of management, measures used, follow-up duration and follow-up methods, and outcome should be recorded in detail for SAEs.

10. Storage of Biological Samples and Measurement

10.1 Biological samples that may be collected during the study

- Primary and/or recurrent/metastatic tumor tissues
- Blood before and during treatment

10.2. Proposed test items

- [name] laboratory will contact relevant sequencing companies for whole-exome sequencing of tumor tissues
- [name] laboratory will perform immunohistochemistry and immunofluorescence (including but not limited to PD-1, PD-L1, and lymphocyte molecular markers such as CD4, CD8) on tumor tissues
- [name] laboratory will carry out methylation tests of tumor tissues

- [name] laboratory will perform ELISA, plasma free nucleotide test, and flow cytometry of patients' blood samples.

10.3 Sample storage and post-processing

Patients' samples will be stored in [name] laboratory. After the clinical trial has ended, these samples may be used for related fundamental studies.

11 Data management and statistical analysis

11.1 Definition of statistical analysis sets

Full analysis set (FAS): Analysis of all enrolled patients who took at least one dose of the drug will be performed according to the intent-to-treat principle. The last observation carried forward is used for patients whose data were not captured for the entire duration of the study.

Per-protocol set (PPS): All patients who completed 2 cycles or more of treatment, conformed to the study protocol, had good compliance, did not use prohibited drugs during the study, and whose case report forms are completed as required. No imputation will be performed for missing data. Statistical analysis of FAS and PPS are simultaneously performed for drug efficacy analysis.

Safety analysis set (SAS): All enrolled patients who had at least taken one dose of the study drug and whose safety after drug administration had been recorded. This dataset will be used for safety analysis.

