	
significant clinically rapid progression or patients with an unstable general condition.
 
 3. The cumulative treatment period with anti-PD-1 antibody reaches 2 years; 4. Radiological examination shows that drug discontinuation can be considered for CR subjects who have completed 6 cycles of drug administration. 5. Intolerable toxicity; 6. Poor compliance; 7. Loss to follow-up. 8. The investigator considers that the subject must withdraw from the study.
Treatment regimen	
IBI308: Product name (sintilimab), 200 mg intravenous infusion, qd, d1, q3w,
 
Anlotinib: 12 mg/tablet, one tablet daily, orally half an hour before breakfast, d1–d14, and 1 treatment cycle lasting 3 weeks. The patient will take the study drug until protocol-stipulated treatment withdrawal criteria are fulfilled.

Sample size calculation Statistical methods	
Simon's 2-stage design was used for sample size estimation. An alpha of 0.05 (one-tailed), a beta of 0.2, and a power of 0.8 were used. Based on existing literature, the objective response rate (ORR) of anti-PD-1 monoclonal antibody monotherapy in advanced or PD-L1-positive recurrent endometrial carcinoma after failure of first-line chemotherapy is 13%.
 
Assuming that IBI308 combined with anlotinib can increase efficacy by 26%, the ORR is 39%. At least 23 patients are needed. Seven patients will be enrolled in stage 1. When the number of valid patients < 2, combination therapy is considered not superior to monotherapy, and this trial will be terminated. Otherwise, 16 subjects will be enrolled in stage 2. The trial is rejected if there are ≤5 patients with ORR in the two stages. Percentages, χ^2 test, and analysis of variance are used to analyze efficacy. Descriptive methods and percentages will be used for safety analysis.

Efficacy evaluation	
RECIST (v1.1) and irRECIST criteria are used for radiologic tumor evaluation after the 2nd treatment cycle (\pm 7 days) and after week 4 (\pm 7 days) after the start of dosing. Subsequently, radiologic tumor evaluation will be performed once every 3 treatment cycles (\pm 7 days) until the 10th cycle. After the 10th cycle, radiologic tumor evaluation will be performed every 4

	treatment cycles (\pm 7 days). Additional examinations can be performed if clinical progression occurs.

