3.1. Overall design

This is a prospective, single-arm, open-label phase II clinical trial in which IBI308 intravenous chemotherapy is combined with oral administration of anlotinib for recurrent or advanced endometrial cancer. The primary objective is to assess the ORR of IBI308 intravenous chemotherapy combined with anlotinib for recurrent or advanced endometrial cancer in patients who failed first-line chemotherapy based on the irRECIST and RECIST 1.1 criteria. Subjects will receive IBI308 200 mg intravenously q3w and anlotinib 12 mg qd d1–

d14 q3w po until a protocol-stipulated treatment termination event occurs. Subject visits will continue after treatment has ended.

Evaluation is performed once after the 2nd treatment cycle (C3) and once after the 4th treatment cycle (C5) since the first dose. Subsequently, an evaluation will be performed once after the 7th treatment cycle (C8) and once after the 10th treatment cycle (C11). After the 10th cycle, an evaluation will be performed once every 4 treatment cycles, and the time window for radiologic evaluation is ± 7 days.

Simon's 2-stage design was used for sample size estimation, with an alpha of 0.05 (one-tailed) and a beta of 0.2 (power of 0.8). Based on existing literature, the ORR of anti-PD-1 monoclonal antibody monotherapy for advanced or recurrent PD-L1-positive endometrial carcinoma in patients who failed first-line chemotherapy is 13%. Assuming that a combination of IBI308 and anlotinib can increase efficacy by 26%, the overall ORR is 39%. The data from at least 23 patients are required to obtain results. Seven patients will be enrolled in stage 1. When the number of valid patients ≤ 1 , combination therapy will be considered not superior to monotherapy, and this trial will be terminated. Otherwise, 16 subjects will be enrolled in stage 2. The trial is rejected if the total number of patients with ORR in the two stages is ≤ 5 .

The intention-to-treat principle will be adopted in the efficacy analysis, and all enrolled subjects will be included. Frequency and percentage will be used for categorical data, and the χ^2 test or exact probability will be used for intergroup comparison. Mean and standard deviation (or median and interquartile range) will be used for quantitative data. The t-test or a non-parametric test will be used for intergroup comparison, the K-M method for survival estimation, and the log-rank test for intergroup comparison.

4. Trial Population

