9.4 Endpoint criteria

Primary endpoint:

Objective response rate (ORR): Defined as the proportion of patients whose tumor volume shrunk to the pre-stipulated value and maintained for more than 4 weeks; i.e., ORR = CR +

PR. The internationally accepted RECIST 1.1 and irRECIST criteria are used for solid tumor evaluation. ORR is used as the primary endpoint for the clinical trial.

Secondary endpoints:

Duration of response (DoR): Time from first evaluation of CR or PR until evaluation of PD or death from any cause. For patients who did not experience PD or death, the last radiologic tumor evaluation date will be the censor date.

Disease control rate (DCR): The proportion of subjects with CR, PR, or SD based on RECIST 1.1 criteria in the analysis set.

Time to response (TTR): Time from start of treatment to first objective response (CR or PR). For patients that did not experience CR or PR, the last radiologic tumor evaluation date will be the censor date.

Progression-free survival (PFS): Defined as time from subject enrollment to tumor progression or death.

Overall survival (OS): Time from start of treatment to death. If the subject is still alive at the end of the study, the “last known date of subject survival” will be the censor date.

12-month OS rate: The proportion of patients that are alive at month 12 after starting treatment.

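### Section 11.1 prescribes last observation carried forward for the full analysis set without limiting it to any endpoint, against the response and survival definitions in 9.4, and the analysis set itself is defined inconsistently

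*Protocol*

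**What the plan says.** **Missing data.** Section 11.1, in the definition of the FAS: "The last observation carried forward is used for patients whose data were not captured for the entire duration of the study". No endpoint is named and none is exempted.

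**Endpoints.** Section 9.4 defines the objective response rate (ORR) through shrinkage "maintained for more than 4 weeks", and section 9.3 also builds a 4-week requirement into complete and partial response. Section 9.4 censors overall survival (OS) at the last date the patient was known to be alive. The 12-month OS rate, however, is worded as a plain proportion: "The proportion of patients that are alive at month 12 after starting treatment". Section 11.2 gives Kaplan-Meier for time-to-event analyses, but for landmark probabilities it names only progression-free survival.

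**Analysis sets.** Section 3.1: "The intention-to-treat principle will be adopted in the efficacy analysis, and all enrolled subjects will be included". Section 11.1 limits the FAS to enrolled patients who took at least one dose. Section 11.2 defines the FAS as everyone included and assigns it to efficacy. The per-protocol set (PPS) in 11.1 begins with "All patients who completed 2 cycles or more of treatment" and adds compliance, absence of prohibited drugs and a completed case report form. Section 11.1 then says: "Statistical analysis of FAS and PPS are simultaneously performed for drug efficacy analysis". It does not call the PPS supportive.

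**Decision rule.** The synopsis and section 3.1 set a Simon two-stage design for 13% against 39%: stop at 1 or fewer responders among 7, reject at 5 or fewer among 23.

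**The concern.** A carry-forward rule replaces what was not observed with the last thing that was. For a response that must be maintained, the unobserved part is exactly what the definition asks for. For survival, the last observation before loss is always that the patient was alive. The rule therefore supplies the favourable answer in both cases, against what 9.4 requires.

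The situation is realistic here. Under section 9.1 scans follow cycles 2, 4, 7 and 10, and then every 4 cycles. With 3-week cycles, the next scheduled scan after a first partial response is 6 to 12 weeks away. Section 4.4 withdraws patients for toxicity, serious adverse events, poor compliance or loss to follow-up, so some may have one responding scan and no later one.

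The decision in this single-arm trial rests on a small count, and one responder can change it. The denominator of the reported ORR is also unsettled, because the set that carries the decision is described in three places in terms that do not agree.

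**Working it through.** **1. The plan's own design.** Inputs from the synopsis and 3.1: p0 = 0.13, p1 = 0.39, n1 = 7, r1 = 1, N = 23, r = 5, one-sided alpha 0.05, power 0.8. The probability of declaring success at true rate p is

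Σ (x = 2 to 7) P(X = x) × P(Y ≥ 6 − x), with X ~ Bin(7, p) and Y ~ Bin(16, p).

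- p = 0.13: 0.0456 (type I error); probability of stopping at stage 1 is 0.772.
- p = 0.39: 0.8003 (power).

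The stated design reproduces, so the sample size is not at fault.

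**2. Carry-forward and ORR.** By last observation:

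- No post-baseline scan: the baseline state is carried; still a non-responder.
- Last scan stable or progressive, with no earlier response: still a non-responder.
- First partial response at the last scan, nothing later: not a response under 9.4, but a response if the scan is carried forward.

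Only the third case matters. One such patient turns 5/23 = 21.7% (reject) into 6/23 = 26.1% (pass), or at stage 1 turns 1/7 (stop) into 2/7 (continue).

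The protocol gives no rate for such patients. Assume carried responses add a fixed amount to a true 13% in both stages, and use the same formula:

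| Added | Rate used | Type I error |
|---|---|---|
| 0 | 0.13 | 0.046 |
| 2 points | 0.15 | 0.080 |
| 3 points | 0.16 | 0.102 |
| 5 points | 0.18 | 0.153 |

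**3. Carry-forward and disease control.** Section 9.4 sets no minimum duration for stable disease, so one stable scan counts with or without the rule. The rate rises only if an unscanned patient's baseline is read as stable disease. Each such patient would add 1/23 = 4.3 points.

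**4. Carry-forward and 12-month OS.** Assume a true rate of 50% (exponential, median 12 months, the lower end of the 12–15 months in section 1.3) and a fraction l lost uniformly over the 12 months. Mean survival over that period is (1 − 0.5)/ln 2 = 0.721. The crude proportion with lost patients carried as alive is

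(1 − l) × 0.5 + l × 0.721.

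For l = 15%: 0.425 + 0.108 = 0.533. For l = 5% and 20%: 0.511 and 0.544. If all losses fell at the very start, the ceiling is (1 − l) × 0.5 + l, which is 0.525, 0.575 and 0.600 for 5%, 15% and 20%. Kaplan-Meier with the 9.4 censoring targets 0.50, provided loss is unrelated to prognosis.

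**5. PPS.** Assume early leavers are non-responders and hold responders at 6. Clopper-Pearson 95% intervals:

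| Excluded | ORR | 95% CI |
|---|---|---|
| 0 | 6/23 = 26.1% | 10.2–48.4 |
| 2 | 6/21 = 28.6% | 11.3–52.2 |
| 3 | 6/20 = 30.0% | 11.9–54.3 |
| 5 | 6/18 = 33.3% | 13.3–59.0 |

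With five exclusions the lower limit passes 13%. The count stays at 6 throughout.

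**The case against.** **Specific rules should override the general sentence.** Sections 9.3 and 9.4 build the 4-week requirement into response, 9.4 censors OS, and 11.2 prescribes Kaplan-Meier. A careful analyst might never apply carry-forward to these endpoints. That is a fair reading, but the protocol does not state an order of precedence, and 11.1 puts the rule in the definition of the efficacy set. A separate statistical analysis plan could narrow it; the protocol's rule would still be wrong as stated.

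**Carry-forward does not generally raise ORR.** A reader might infer that it lifts ORR, disease control and survival across the board. It does not. ORR moves only through unconfirmed last-scan responses, and survival only if the crude proportion for the 12-month rate is used. That rate is a secondary endpoint and is absent from the synopsis list. This part of the objection stands in full.

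**The PPS cannot break the Simon error rates.** The rule counts responders, and no replacement of patients is stated. Excluding patients leaves the count unchanged or lowers it, so it cannot create a false success. This also stands. A percentage that passes 39% after exclusions proves nothing, because 39% is the design alternative and not a success threshold.

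**The full set already leads.** Sections 3.1 and 11.2 direct efficacy to all enrolled or included patients, and reporting a PPS beside it is ordinary practice. Reading the two sets as equal in rank goes beyond the text. What remains is that 11.1 does not subordinate the PPS. Its 2-cycle threshold falls where the first scan is due: a patient progressing at that scan is not dropped by this criterion, but one who leaves before it is.

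**Quality of life is measured repeatedly.** The sentence might be meant for it. The case here covers response, disease control and survival only.

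**Conclusion.** The point holds in this limited form. The carry-forward sentence in 11.1 has no endpoint limit and conflicts with 9.4. Applied as written, one unconfirmed response can reverse the final decision. Type I error would be 0.080 to 0.153 instead of 0.046 if carried responses add 2 to 5 points to a true 13%; that range is an assumption. The effect on 12-month OS is about 3 points under an assumed 15% uniform loss, and arises only with the crude proportion.

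The inconsistent FAS definition is a separate defect of wording and rests on no assumption. The PPS is a reporting matter: it can raise the percentage and its interval, but it does not threaten the 1/7 and 5/23 rules. The documents do not support a stronger claim that both rules bias every efficacy endpoint upward or that the design itself is unsound. The stated rule should still be corrected before the response decision is made.

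**What to change.** - In 11.1, remove last observation carried forward for ORR, disease control and all survival endpoints.
- Use one FAS definition in 3.1, 11.1 and 11.2, and name it as the set for the 1/7 and 5/23 decisions.
- State in 9.4 and 11.2 that a patient without a confirmed response, including one with no evaluable post-baseline scan, counts as a non-responder.
- Label the PPS in 11.1 as supportive.
- Define the 12-month OS rate in 9.4 as the Kaplan-Meier estimate, with the censoring already given there for OS.

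The cost is wording in four sections, with no extra patients or visits. The reported ORR may be slightly lower. With non-responder counting, the design keeps its exact type I error of 0.0456 and power of 0.8003 at the stated rates of confirmed response.

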11.2. Statistical analysis plan

Baseline data will be analyzed based on the FAS. Full analysis set (defined as all included patients) and safety analysis set (defined as patients had at least one cycle of treatment) were used for efficacy analysis and safety analysis, respectively. In general, categorical data will be summarized using number of patients (n), frequency and percentages. Two-sided exact 95% confidence intervals (CIs) based on the Clopper-Pearson method will be provided to summarize the binomial proportion of the ORR and DCR for both RECISTv1.1 and irRECIST assessments where applicable. Continuous data will be summarized using the number of patients, mean, standard deviation, median, first and third quartiles (Q1, Q3), minimum, and maximum. Time-to-event analyses will be performed using Kaplan-Meier (KM) methods. Medians of PFS and DOR were analyzed using the Kaplan-Meier curve, and 95% CIs were calculated with a generalized Brookmeyer and Crowley method. We calculated the probabilities of patients achieving a PFS > 6 months or > 12 months using the Kaplan-Meier product-limit method, and reverse Kaplan-Meier calculated the Greenwood Formula Follow-up time. Cox regression models were used to test the association between clinicopathologic and genetic characteristics and PFS, and a P-value < 0.05 was considered significant. For genomic analysis, P-value < 0.1 was considered statistically significant. All statistical analyses

about clinical listings will be performed using SAS v9.4 or higher. Gene analysis will be performed using R V4.1.0 or higher

12. Ethical Standards

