4.3. Removal criteria

Subjects enrolled in this trial who meet one of the following criteria will be removed:

(1) Enrolled subjects who do not satisfy the inclusion criteria/satisfy the exclusion criteria and are wrongly enrolled.

(2) Subjects with serious protocol violations.

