6.1. Overall principles

Dose modification must be based on the most severe drug toxicity that occurred in the previous dosing cycle. Three days before each dosing of the investigational drug on Day 1, the blood, liver, and renal function test results of the subject must meet the dosing requirements. All other toxicities must be resolved to CTCAE v4.03 Grade 0–1 or baseline

level (except for alopecia, fatigue, special regulations in the protocol, or other conditions that are deemed not clinically significant by the investigator). If the subject is not dosed as scheduled due to drug toxicity, the next dose can be delayed. If an investigational drug needs to be suspended/permanently discontinued due to investigational drug-related toxicity or other reasons, other investigational drug(s) can be used independently if the corresponding criteria are met. All dose modifications must be recorded in the file, including the reason and management.

AEs related to sintilimab exposure may stem from immunological etiologies. These immune-related AEs (irAEs) may occur within a short period after the first dose or several months after the last dose of sintilimab. They may affect more than one system simultaneously. Based on existing clinical trial data, most irAEs are reversible and can be managed by drug dosing interruption, administration of glucocorticoids, and/or other supportive treatments. For suspected irAEs, an appropriate evaluation must be performed to confirm the etiology or rule out other causes. Other procedures or tests, such as bronchoscopy, endoscopy, or skin biopsy, can be included in this evaluation. Sintilimab will be suspended or permanently discontinued, and glucocorticoids will be administered based on irAE severity. For dose modification and toxicity management guidelines for potential irAE, please refer to the “Management manual for immune-related adverse event” provided by the pharmaceutical company.

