9.5.1 Definition of adverse events

Adverse event (AE): An adverse event refers to any untoward medical event that occurs in a clinical trial subject after receiving a drug and does not necessarily have a causal relationship with the treatment. Any untoward medical event from the moment the subject signed the informed consent form and received the investigational drug to 1 month after the treatment has ended is considered an AE, regardless of whether it has a causal relationship with the investigational drug.

Serious adverse event (SAE): refers to an AE that occurs at any dose of the investigational drug or at any time during the observation period that requires hospitalization, prolongation of hospitalization, permanent or serious disability or causing life-threatening events, death, a congenital anomaly or deformity.

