9.5.2. Adverse event determination criteria

Adverse reactions should be assessed based on the Common Terminology Criteria for AEs (NCI CTCAE v4.03 grading criteria). The following criteria can be used to assess AEs that are not listed in the NCI toxicity grading criteria:

- Grade 1 (mild): the presence of discomfort that does not affect normal daily activities;
- Grade 2 (moderate): severity of discomfort insufficient to decrease or affect normal daily activities;
- Grade 3 (severe): Unable to work or carry out normal daily activities;
- Grade 4 (fatal): results in disability or death.

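### Section 11.2 limits the safety set to patients with at least one cycle, contradicting the one-dose definition in 11.1; the efficacy set and the section 4.3 removal rule also need reconciling

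*Protocol*

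**What the plan says.** **Safety set.** Section 11.1 defines it as "All enrolled patients who had at least taken one dose of the study drug and whose safety after drug administration had been recorded" and assigns it to the safety analysis. Section 11.2 assigns to the same analysis a "safety analysis set (defined as patients had at least one cycle of treatment". The synopsis gives a cycle as 3 weeks.

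**Efficacy set.** Section 3.1 states: "The intention-to-treat principle will be adopted in the efficacy analysis, and all enrolled subjects will be included". Section 11.1 limits the FAS to enrolled patients with at least one dose. Section 11.2 describes the FAS as all included patients and names it as the set for efficacy. Section 11.1 adds: "Statistical analysis of FAS and PPS are simultaneously performed for drug efficacy analysis". The PPS requires two or more completed cycles, good compliance and no prohibited drugs.

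**Removal.** Section 4.3 reads: "Subjects enrolled in this trial who meet one of the following criteria will be removed". The criteria are wrong enrolment and serious protocol violations. The latter are not defined, and the section does not say whether removal is from treatment, from analysis or from both.

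**Decision rule.** Sections 3.1 and the synopsis set 7 patients in stage 1 (stop at 1 or fewer responders) and 16 in stage 2 (unsuccessful at 5 or fewer responders in 23).

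**The concern.** The two safety definitions disagree about exactly one group: patients who were dosed but did not receive a cycle of treatment. The protocol itself produces such patients. Section 4.4 withdraws subjects for serious adverse events, intolerable toxicity and death, and the infusion-reaction table in section 6.3 ends treatment after a Grade 3 or 4 reaction, which can happen at the first infusion. Table 1 collects adverse events from consent onward, so these events would be recorded and then left out of the 11.2 set. The patients lost are selected by toxicity, so the bias has a known direction. Safety of the combination is a stated objective, and in a trial of 23 each patient carries more than 4 percentage points (1/23 = 4.3%).

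On the efficacy side the problem is ambiguity. An open-label trial with an undefined violation category and a removal rule of unclear scope lets the ORR denominator be settled after responses are known. That cannot be squared with the statement in section 3.1 that every enrolled subject is included.

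**Working it through.** **1. The plan's own figure.** Inputs from section 3.1: null ORR 0.13, alternative 0.39, success if X1 > 1 of 7 and total > 5 of 23. The exact probability of success is the sum over x = 2 to 7 of P(X1 = x) × P(X2 > 5 − x), with X1 ~ Bin(7, p) and X2 ~ Bin(16, p).
- At p = 0.13: 0.0456, with probability of early stopping 0.772.
- At p = 0.39: 0.8003.

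The stated one-sided 0.05 and power 0.8 reproduce, so the sample size is not in question.

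**2. Safety denominator.** Suppose e of n dosed patients have a given event and k of those e stop in cycle 1. The one-dose set reports e/n and the one-cycle set reports (e − k)/(n − k). The shortfall is k(n − e)/[n(n − k)]. The values of e and k are assumptions; the protocol gives none.

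| e | k | One-dose set | One-cycle set | Shortfall (points) |
|---|---|---|---|---|
| 5 | 2 | 5/23 = 21.7% | 3/21 = 14.3% | 7.5 |
| 8 | 1 | 8/23 = 34.8% | 7/22 = 31.8% | 3.0 |
| 8 | 2 | 8/23 = 34.8% | 6/21 = 28.6% | 6.2 |
| 8 | 3 | 8/23 = 34.8% | 5/20 = 25.0% | 9.8 |

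**3. ORR denominator.** Take 6 responders, the smallest successful count, and m non-responders removed under section 4.3 without replacement. The ORR is 6/(23 − m).
- m = 0: 26.1% (Clopper-Pearson 95% CI 10.2 to 48.4)
- m = 1: 27.3%
- m = 2: 28.6%
- m = 3: 30.0% (11.9 to 54.3)

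**4. Decision rule.** The rule is a count of responders. Removing non-responders without replacement leaves that count as it was, so the decision is the same. If removal were unrelated to response and 3 stage 2 patients were lost (7 then 13, still more than 5 needed), the exact type I error would be 0.028 and power 0.755. That is conservative rather than inflated.

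**5. The three FAS wordings.** If included is read as enrolled, sections 3.1 and 11.2 agree, and 11.1 differs from them only for patients enrolled but never dosed.

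**The case against.** It can be argued that section 11.1, whose title says it defines the analysis sets, governs, and that 11.2 is a loose paraphrase; at least one cycle might even be meant to include a cycle merely started. That is possible, but 11.2 offers its wording as a definition, and nothing ranks the two sections. The contradiction stands. The counts in the safety illustration are assumed, and that stands too: they show scale, not a forecast.

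The efficacy half is fairly contested. Sections 3.1 and 11.2 drop no one, 11.2 names the FAS for efficacy, and section 3.1 counts the stages by enrolment. The 4.3 criteria concern eligibility and conduct, not outcome. All of this stands, and what remains is a reconciliation of wording.

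Three stronger readings are tempting and are not supported:
- *Removal inflates the type I error.* If 10% or 20% of enrolled patients were non-responders who were removed and replaced, the null rate would become 0.13/0.9 = 0.144 or 0.13/0.8 = 0.1625, and the exact error 0.069 or 0.107. No passage provides for replacement.
- *Both defects discard the worst outcomes.* This fits the one-cycle safety set, and the PPS loses early failures through its two-cycle condition. It does not fit the FAS or the 4.3 criteria.
- *The adverse-event window is an error.* Section 6.1 says immune-related events "may occur within a short period after the first dose or several months after the last dose of sintilimab", and section 9.5.1 counts events "to 1 month after the treatment has ended is considered an AE". The first describes when events can occur, the second when they are collected. A longer window is a design preference; the two texts do not conflict.

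**Conclusion.** The safety-set definition in section 11.2 is wrong as written. It contradicts 11.1 and, if followed, understates toxicity. The shortfall is about 3 to 10 percentage points in the examples above, assuming that one to three patients with a severe event stop in the first cycle and that one cycle means a cycle received. If no dosed patient stops in cycle 1, the two definitions give the same result, apart from 11.1's requirement of recorded safety data.

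The efficacy set is inconsistently worded, and section 4.3 is not reconciled with the inclusion of all enrolled subjects. The exposure is in the ORR estimate, about 4 points if 3 non-responders leave the denominator. It is not in the go/no-go count, and the 7/23 design is unaffected.

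A separate, minor slip: the fallback scale in section 9.5.2 describes Grade 2 as "severity of discomfort insufficient to decrease or affect normal daily activities", which does not differ from Grade 1 in its effect on daily life. It applies only to events not listed in CTCAE v4.03 and has no bearing on the analysis sets.

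**What to change.** 1. Define the safety set once, in 11.1, as all patients who received at least one dose of either study drug, and delete the one-cycle definition from 11.2.
2. Use one FAS definition in 3.1, 11.1 and 11.2. Tie the primary ORR and the 7 and 23 counts to it, with non-evaluable patients counted as non-responders.
3. State in 4.3 that subjects meeting its criteria leave only the PPS and stay in the FAS and the safety set.
4. Label the PPS analysis supportive.
5. As a separate correction, reword the fallback Grade 2 text in 9.5.2 so that it is distinct from Grade 1.

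The cost is protocol wording only, with no extra patients, visits or data. The reported ORR may be slightly lower than one computed after removals.
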